4.6 Exploratory endpoints and Protocol for Exploratory Analysis

See Lab Manual for details of specimen collection and storage.

1. To examine changes in STAT1 phosphorylation and MHC1 up regulation in PBMCs as an indicator of IFN activity
 - a. STAT1 phosphorylation by immunoblot analysis. PBMCs will be isolated from patient blood by Ficoll-Paque Plus-based centrifugal separation (GE Healthcare Bio-Sciences, Uppsala, Sweden) and cryopreserved. The phosphorylated (p) form of STAT1 (Tyr701) as well as total STAT1 in cryopreserved PBMC pellets will be measured by immunoblot analysis and/or by intracellular flow cytometry performed on fresh PBMC. For immunoblot analysis, Whole-cell extracts from PBMCs (5×10^5) will be prepared in TL buffer (1% [v/v] Triton-X100, 150 mM NaCl, 20 mM HEPES [pH 7.3], 5 mM EDTA, 5 mM NaF, 0.2 mM NaVO₃ [*ortho*], and Complete Protease Inhibitor cocktail [Roche]) and clarified by centrifugation (15000×g, 10 minutes at 4°C). Samples will be denatured by boiling in Laemmli buffer (0.1% [v/v] 2-mercaptoethanol, 0.0005% [w/v] bromophenol blue, 10% [v/v] glycerol, 2% [w/v] SDS, 63 mM Tris-HCl [pH 6.8]) for 2 minutes and separated by 12% SDS-PAGE. Protein from gels will be transferred onto PVDF membranes (Millipore) and blocked in blocking buffer (0.1% [v/v] Tween20, 5% [w/v] non-fat dry milk in PBS) at room temperature for 15 minutes. Blots will be incubated for at least 18 h at 4°C with primary antibody (p-STAT1, 1:500 (Upstate); total STAT1, 1:2000 (BD

Pharmingen) diluted in blocking buffer, followed by 3 washes for 10 minutes each in washing buffer (0.1% [v/v] Tween 20 in PBS) at room temperature. Next, blots will be incubated with secondary antibody (horseradish peroxidase-conjugated goat anti-rabbit/mouse IgG (H+L), 1:5000, Jackson ImmunoResearch) for at least 18 h at 4°C, followed by 3 washes of 10 minutes each in washing buffer at room temperature. Blots will then be incubated in enhanced chemiluminescence substrate (Pierce ECL Plus Western Blotting Substrate, Pierce) for one minute, and proteins will be detected by chemiluminescence using X-ray film (Denville Scientific Inc.).

- b. STAT1 phosphorylation by intracellular flow cytometry. Fresh PBMCs (5×10^5 cells) obtained from patients will be suspended in 100 μ L of RPMI-1640 medium supplemented with 10% FBS, fixed by incubating in 100 μ L of Fix & Perm Reagent A (Caltag Laboratories, Burlingame, CA) for 2–3 minutes at room temperature, and incubated for 10 minutes in 3 mL of cold methanol. Cells will then be washed in flow buffer (PBS supplemented with 5% FBS) and permeabilized with 100 μ L of Fix & Perm Reagent B (Caltag Laboratories). Cells will then be incubated for a total of 30 minutes at room temperature in Fix & Perm Reagent B containing 1 μ g of a mouse anti-human FITC-conjugated anti-pSTAT1 antibody (BD Pharmingen) or an appropriate conjugated isotype control antibody. Fluorescence staining data will be acquired on a BD FACSaria II, which is calibrated daily for clinical use. Data will be processed with FlowJo software.
- c. MHC1 upregulation by flow cytometry. Fresh PBMCs Cells will then be stained using fluorophore-conjugated pan-MHC-I specific antibody (clone W6/32, DAKO) or an appropriate isotype control. Fluorescence staining data will be acquired on a BD FACSaria II, which is calibrated daily for clinical use. Data will be processed with FlowJo software.

2. To use archived FFPE tumor tissue to correlate activated tissue stroma (i.e., desmoplasia) with IL-6 and patient outcomes

The [name] lab has observed that *in vivo* stromal activation (measured by a specific stromal isoform of the actin binding protein palladin) corresponds to worse outcomes regardless of grade or stage of the tumor in RCC.⁵¹ Also, using stromal (patient derived tumors) ECMs they have observed increased tumoral IL-6 and NF- κ B signaling ([name] unpublished results). We will thus examine the correlation between activated stroma (by assessing palladin IHC levels, as published by [name] and briefly described below, in the primary renal tumor, a metastasectomy sample or a biopsy) and plasma levels of IL-6 (using ELISA based assays) with patient outcome and response to treatment a la previous work. We want to answer whether activated stroma could predispose for increased IL-6 levels and whether both together will present a better response to the proposed combination treatment. The rationale behind this is that patients with high desmoplasia (represented by plasma IL-6 levels) will not only be at increased risk of worse outcome and recurrence but the same patients may also present better responses to

the combinational treatment approach.

Immunohistochemistry of paraffin-embedded samples will be performed using rabbit anti-palladin (1:100) antibody. A hybridoma via an MTA agreement is also in place and thus unlimited access to monoclonal antibody is available. An avidin biotin-peroxide kit (Vectastain Elite; Vector Laboratories, Burlingame, CA), together with chromogen 3',3'-diaminobenzidine, was used following manufacturer's instructions. Negative controls will consist of treated samples incubated using iso-matched non-specific primary antibodies and normal rabbit or mouse pre-immune sera. All sections will be counterstained with hematoxylin and mounted for inspection. The score for the intensity of staining in the immunohistochemistry will be performed by a 'blinded' pathologist using semiquantitative measurements. The assigned intensities consist of four categories; 0, 0.5, 1, and 2. Absence of staining will be assigned with the lowest value (0) and the strongest set of intensities will be assigned the highest (2). The correlation between immunohistological staining and clinical parameters and outcomes will be analyzed.

Serum levels of IL-6 will be assessed using ELISA. Sera will be procured via centrifugation of peripheral blood samples of study patients and stored at -80° until analysis. Sera samples will be thawed at room temperature and then assayed in duplicate wells using the premixed Bio-Plex® Pro Human Cytokine Array (Bio-Rad) according to manufacturer's instructions.

3. To use archived FFPE from past biopsies for IHC analysis of nuclear NF-κB p65 and STAT1

FFPE sections will be cut to a thickness of 4 microns, deparaffinized by xylene, and rehydrated in decreasing concentration of ethanol. Antigen retrieval will be achieved by boiling sections in 10mM citrate buffer for 20 minutes. After blocking of endogenous peroxidase with 3% hydrogen peroxidase in methanol, sections will be incubated with Background Sniper (Biocare Medical) at room temperature for 30 minutes. The sections will next be incubated with primary antibodies, NF-κB p65 (Cell Signaling) at a dilution of 1:500, and STAT1 (BD Biosciences) at a dilution of 1:100, at 4°C overnight. After washing in PBS, sections will be incubated with Labeled Polymer-HRP anti-rabbit and anti-mouse (DAKO) secondary antibody at RT for 1h, exposed to diaminobenzidine tetrahydrochloride solution, and counterstained with hematoxylin. After dehydrating in increasing concentrations of ethanol and clearing in xylene, sections will be mounted in Permount. Images will be taken on a Nikon Eclipse E600 microscope with NIS Elements D3.0 software and scored across multiple fields for percentage of cells with nuclear NF-κB or STAT1. Only nuclear staining for p65 and STAT1 are demonstrative of activity and thus only nuclear staining will be scored.

5. STUDY POPULATION

5.1 Inclusion Criteria

Each patient must meet all of the following inclusion criteria to be enrolled in the study:

1. Male or female patients 18 years or older.
2. Voluntary written consent must be given before performance of any study related procedure not part of standard medical care, with the understanding that consent may be withdrawn by the patient at any time without prejudice to future medical care.
3. Female patients must be:
 - Postmenopausal for at least 1 year before the screening visit, OR
 - Surgically sterile, OR
 - If they are of childbearing potential, agree to practice 2 effective methods of contraception, at the same time, from the time of signing the informed consent form through 90 days after the last dose of study drug, OR
 - Agree to practice true abstinence when this is in line with the preferred and usual lifestyle of the subject. (Periodic abstinence [eg, calendar, ovulation, symptothermal, post-ovulation methods] and withdrawal are not acceptable methods of contraception.)
4. Male patients, even if surgically sterilized (ie, status post-vasectomy), must agree to practice effective barrier contraception during the entire study treatment period and through 90 days after the last dose of study drug, or agree to practice true abstinence when this is in line with the preferred and usual lifestyle of the subject. (Periodic abstinence [eg, calendar, ovulation, symptothermal, post-ovulation methods] and withdrawal are not acceptable methods of contraception.)
5. Patients must have a diagnosis of a metastatic renal cell carcinoma with a $\geq 50\%$ clear cell component.
6. Eastern Cooperative Oncology Group (ECOG) performance status 0, 1, or 2.
7. Patients must meet the following clinical laboratory criteria:
 - Absolute neutrophil count (ANC) $\geq 1,000/\text{mm}^3$ and platelet count $\geq 100,000/\text{mm}^3$ and hemoglobin $\geq 9 \text{ g/dL}$. Platelet or red cell transfusions to help patients meet eligibility criteria are not allowed within 3 days before study enrollment.
 - Total bilirubin $\leq 1.5 \times$ the upper limit of the normal range (ULN).

- Alanine aminotransferase (ALT) and aspartate aminotransferase (AST) $\leq 3 \times$ ULN.
- Calculated by Cockcroft-Gault or measured by 24 hour urine creatinine clearance ≥ 50 mL/min (see Section 12.2).

8. Measurable disease by RECIST 1.1.
9. Receipt of at least two line of prior therapy for metastatic RCC.
10. Patients with stable brain metastasis are eligible provided they received definitive therapy (EBRT, gamma knife, surgery) no sooner than 14 days prior to registration and are off all steroids.

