5.2 Exclusion Criteria

Patients meeting any of the following exclusion criteria are not to be enrolled in the study:

1. Female patients who are lactating or have a positive serum pregnancy test during the screening period.
2. Failure to have fully recovered (ie, \leq Grade 1 toxicity) from the reversible effects of prior chemotherapy, radiation therapy or targeted therapy
3. Previous use of interferon, ixazomib or bortezomib.
4. Washout periods for prior therapy are as follows
 - Bevacizumab – last dose must be \geq 6 weeks prior to day 1 of study treatment.
 - Targeted therapy – last dose must be \geq 5 half-lives prior to initiation of day 1 of study treatment.
 - Other chemotherapy, immunotherapy, or radiotherapy – Last dose must be \leq 3 weeks prior to day 1 of study treatment
5. Major surgery within 14 days before enrollment.
6. Radiotherapy within 14 days before enrollment. If the involved field is small, 7 days will be considered a sufficient interval between treatment and administration of the Ixazomib.
7. Untreated central nervous system involvement.
8. Uncontrolled thyroid disease.
9. Infection requiring systemic antibiotic therapy or other serious infection within 14 days before study enrollment.

10. Evidence of current uncontrolled cardiovascular conditions, including uncontrolled hypertension, uncontrolled cardiac arrhythmias, symptomatic congestive heart failure, unstable angina, or myocardial infarction within the past 6 months.
11. Systemic treatment, within 14 days before the first dose of Ixazomib, with strong inhibitors of CYP1A2 (fluvoxamine, enoxacin, ciprofloxacin), strong inhibitors of CYP3A (clarithromycin, telithromycin, itraconazole, voriconazole, ketoconazole, nefazodone, posaconazole) or strong CYP3A inducers (rifampin, rifapentine, rifabutin, carbamazepine, phenytoin, phenobarbital), or use of Ginkgo biloba or St. John's wort.
12. Known ongoing or active systemic infection, active hepatitis B or C virus infection, or known human immunodeficiency virus (HIV) positive.
13. Decompensated liver disease (Child-Pugh score >6) or active or past auto-immune hepatitis.

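### Inclusion 10 does not say whether 14 days since brain-metastasis therapy is a minimum or a maximum; read literally it bars patients treated earlier and largely collides with exclusions 5 and 6

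*Combined protocol and SAP*

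**What the plan says.** Section 5.1, item 10 makes patients with stable brain metastases eligible if they "received definitive therapy (EBRT, gamma knife, surgery) no sooner than 14 days prior to registration and are off all steroids".

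Four items in Section 5.2 bear on the same patients:

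- **Item 4, third bullet** (washout for other chemotherapy, immunotherapy or radiotherapy) is printed with a less-than-or-equal sign: the last dose may be at most "3 weeks prior to day 1 of study treatment". The two bullets above it, for bevacizumab and targeted therapy, set minimum intervals.
- **Item 5** excludes "Major surgery within 14 days before enrollment".
- **Item 6** excludes "Radiotherapy within 14 days before enrollment", with an exception: "If the involved field is small, 7 days will be considered a sufficient interval between treatment and administration of the Ixazomib".
- **Item 7** excludes "Untreated central nervous system involvement".

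Three other places fix the timing. The Schedule of Events (footnote 2) and Section 4.2 give ixazomib in weeks 2 to 4 of each cycle, with week 1 off. Section 5.3.1 asks that treatment begin within 7 days of registration and requires a signed eligibility checklist. Section 4.3 counts a phase II patient as enrolled on cycle 1 day 1, once at least one of the drugs has been given.

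**The concern.** In plain English, sooner means earlier. Therapy given no sooner than day -14 was given on day -14 or later, that is, in the last two weeks. A checklist applied that way refuses a patient who had gamma knife three months ago and is stable and off steroids. It points instead to patients treated in the very period that exclusions 5 and 6 mostly close.

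The stake is who enters the trial. Every inclusion criterion must be met, and the checklist is signed at registration. Depending on how a screener reads item 10, either patients the criterion seems meant to admit are turned away, or they are enrolled against the literal text and become eligibility deviations. Counts are small: under Section 8.1.2 the first stage stops if at most 8 of 17 patients are progression-free at 8 weeks, or if 3 of 17 have unacceptable toxicity. Eligibility should therefore be unambiguous, although nothing in the documents shows that this wording would move those counts.

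**Working it through.** The plan gives no figure to reproduce, so the check is to lay the windows on one time axis.

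**Notation and assumptions**

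- t = days from definitive brain therapy to registration.
- L = days from registration to cycle 1 day 1, from 0 to 7 (Section 5.3.1).
- First ixazomib dose = L + 7 days after registration (week 2 of cycle 1).
- Enrollment is first taken as the registration date; this is relaxed in step 3.

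**1. Literal reading of inclusion 10: t ≤ 14**

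- *Major surgery or larger-field radiotherapy.* Exclusions 5 and 6 remove t < 14, or t ≤ 14 if day 14 counts as within 14 days. What remains is t = 14 only, or no day at all.
- *Small-field radiotherapy (for example gamma knife, if its field counts as small).* Exclusion 6 needs 7 days to ixazomib: t + L + 7 ≥ 7, which holds for every t ≥ 0. All 15 days from 0 to 14 pass. If the 7 days were counted to registration instead, days 7 to 14 would pass (8 of 15).
- *Anyone with t > 14* fails inclusion 10, whatever the therapy.

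**2. Minimum-interval reading: t ≥ 14**

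Every t from 14 onward (15 onward for surgery and larger fields if day 14 counts as within 14 days) passes exclusions 5 and 6. There is no conflict.

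**3. If enrollment means cycle 1 day 1, as Section 4.3 says for phase II**

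Exclusions 5 and 6 then require t + L ≥ 14. With L = 0 the result is as in step 1. With L = 7 the condition is t ≥ 7, so on the literal reading days 7 to 14 pass for major surgery and larger-field radiotherapy too (8 to 14 if the boundary day is excluded). The size of the collision therefore depends on which date enrollment is. The refusal of everyone with t > 14 does not.

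**4. Adding exclusion 4, third bullet, for radiotherapy-treated patients**

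- As printed: t + L ≤ 21. Combined with the minimum-interval reading (t ≥ 14), L = 0 leaves days 14 to 21, and L = 7 leaves day 14 at most.
- The patient with gamma knife three months ago still fails, because three months exceeds 21 days. Rewording inclusion 10 does not admit this patient.
- With the sign reversed (t + L ≥ 21), the bullet agrees in direction with the two above it and admits this patient. It then sets 3 weeks before day 1 for radiotherapy, where exclusion 6 sets 14 days before enrollment, or 7 days before ixazomib for a small field. The two items need reconciling whichever sign is meant.

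**The case against.** The strongest reply is that the phrase is loosely worded and no sensible screener would apply it literally. People do use it to mean that at least 14 days must have passed. The context favours that: the disease must be stable and steroids stopped, exclusions 5 and 6 use the same 14 days as a minimum, and exclusion 7 bars only untreated CNS disease. On that reading the conflict with exclusions 5 and 6 disappears. This largely stands, and the minimum interval is probably what was meant. It does not remove the defect, because the text does not say so and exclusion 4, third bullet, points the other way for radiotherapy.

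A reader might infer more: that inclusion 10 requires therapy in a period that exclusions 5 and 6 forbid outright, so that almost nobody can qualify. The documents do not support this.

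- The requirement is one of two readings.
- Exclusion 6 does not close the whole period, because of its small-field exception, and inclusion 10 names gamma knife.
- The effect is confined to patients with brain metastases, and no count of them is given.

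Nor do the documents support an argument that different sites would enrol different patients. Section 4 describes a single-center study, and Section 5.3.1 registers patients centrally. The real risk is different screeners, or one screener over time. Confusion of recovery from brain therapy with unacceptable toxicity is also a weak argument: the neuropsychiatric component must be grade 4 (Section 4.5), and exclusion 2 already requires recovery to grade 1 or less from the reversible effects of prior radiation.

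**Conclusion.** The concern holds as a fault in operative eligibility text. Taken literally, inclusion 10 rejects every patient whose brain metastases were treated more than 14 days before registration. It also leaves at most day 14 for major surgery or larger-field radiotherapy, provided enrollment is the registration date and the surgery counts as major. If enrollment is cycle 1 day 1 and treatment starts 7 days after registration, up to days 7 to 14 remain. Small-field radiotherapy can pass exclusion 6 on any of days 0 to 14. Taken as a minimum interval, inclusion 10 agrees with exclusions 5 and 6, but exclusion 4, third bullet, as printed, still limits radiotherapy to 21 days before day 1. The text should be clarified. The fault does not alter the sample size, the error rates or the decision rules, and no effect on accrual can be quantified from the documents.

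**What to change.** Reconcile inclusion 10 with exclusions 4 (third bullet), 5 and 6 in one edit:

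1. State in each whether the interval is a minimum or a maximum. If inclusion 10 is meant as a minimum, write that therapy was completed at least the stated number of days before the reference date.
2. Check the direction of the sign in exclusion 4, third bullet, and say how its radiotherapy interval relates to the one in exclusion 6.
3. Count all the windows from one reference date. The text now uses registration, enrollment, day 1 and ixazomib administration, and Section 4.3 defines enrollment separately for phase II.
4. Update the eligibility checklist to match.

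The length of each interval is for the sponsor to decide. The cost is a few words in Sections 5.1 and 5.2 and the matching checklist lines, with no new procedure and no change in sample size.

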5.2 Exclusion Criteria

Patients meeting any of the following exclusion criteria are not to be enrolled in the study:

1. Female patients who are lactating or have a positive serum pregnancy test during the screening period.
2. Failure to have fully recovered (ie, \leq Grade 1 toxicity) from the reversible effects of prior chemotherapy, radiation therapy or targeted therapy
3. Previous use of interferon, ixazomib or bortezomib.
4. Washout periods for prior therapy are as follows
 - Bevacizumab – last dose must be \geq 6 weeks prior to day 1 of study treatment.
 - Targeted therapy – last dose must be \geq 5 half-lives prior to initiation of day 1 of study treatment.
 - Other chemotherapy, immunotherapy, or radiotherapy – Last dose must be \leq 3 weeks prior to day 1 of study treatment
5. Major surgery within 14 days before enrollment.
6. Radiotherapy within 14 days before enrollment. If the involved field is small, 7 days will be considered a sufficient interval between treatment and administration of the Ixazomib.
7. Untreated central nervous system involvement.
8. Uncontrolled thyroid disease.
9. Infection requiring systemic antibiotic therapy or other serious infection within 14 days before study enrollment.

10. Evidence of current uncontrolled cardiovascular conditions, including uncontrolled hypertension, uncontrolled cardiac arrhythmias, symptomatic congestive heart failure, unstable angina, or myocardial infarction within the past 6 months.
11. Systemic treatment, within 14 days before the first dose of Ixazomib, with strong inhibitors of CYP1A2 (fluvoxamine, enoxacin, ciprofloxacin), strong inhibitors of CYP3A (clarithromycin, telithromycin, itraconazole, voriconazole, ketoconazole, nefazodone, posaconazole) or strong CYP3A inducers (rifampin, rifapentine, rifabutin, carbamazepine, phenytoin, phenobarbital), or use of Ginkgo biloba or St. John's wort.
12. Known ongoing or active systemic infection, active hepatitis B or C virus infection, or known human immunodeficiency virus (HIV) positive.
13. Decompensated liver disease (Child-Pugh score >6) or active or past auto-immune hepatitis.
14. Any serious medical or psychiatric illness that could, in the investigator's opinion, potentially interfere with the completion of treatment according to this protocol. In particular, a history of a serious psychiatric illness that might be exacerbated by IFN- α -2b; a history of significant or unstable cardiovascular, hepatic or gastrointestinal disease; a history of autoimmune disease of any kind.
15. Known allergy to any of the study medications, their analogues, or excipients in the various formulations of any agent.
16. Known GI disease or GI procedure that could interfere with the oral absorption or tolerance of ixazomib including difficulty swallowing.
17. Evidence of another clinically or radiographically active invasive malignancy OR Diagnosed or treated for another malignancy within 2 years before study enrollment or previously diagnosed with another malignancy and have any evidence of residual disease. Patients with nonmelanoma skin cancer or carcinoma in situ of any type are not excluded if they have undergone complete resection.
18. Patient has \geq Grade 3 peripheral neuropathy, or Grade 2 peripheral neuropathy with pain on clinical examination during the screening period.
19. Having received an investigational agent with 21 days of receiving the first dose of study drug on this trial.

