1. BACKGROUND AND STUDY RATIONALE

Metastatic Renal Cell Carcinoma

Renal cell carcinoma (RCC) is a relatively rare cancer, comprising only 3.9% of all new cancer cases in the United States, with an estimated incidence of new cancers of the kidney and renal pelvis being 65,150 cases in 2013 and leading to 13,680 deaths.¹ World-wide, RCC is diagnosed in approximately 170,000 individuals each year with over 72, 000 deaths.² Due to a lack of a proven screening intervention and an often clinically silent disease course, RCC often presents in an advanced or metastatic state and over half of RCC patients will at some point develop metastatic renal cell carcinoma (mRCC).³ Once metastatic, RCC is resistant to conventional chemotherapy and radiotherapy.⁴

Over the last decade, advances in translational research have led to a rapid paradigm shift in the management of mRCC patients. With the elucidation of the von Hippel-Lindau/hypoxia-inducible factor (VHL-HIF) and mammalian target of rapamycin (mTOR) pathways in mRCC, seven new drugs have been approved since 2005 and many more are in clinical development.⁵ Currently FDA approved agents include vascular endothelial growth factor (VEGF) receptor tyrosine kinase inhibitors (TKIs) sunitinib, pazopanib, axitinib and sorafenib; the mTOR inhibitors temsirolimus and everolimus, and the anti-VEGF monoclonal antibody bevacizumab.⁶

Due to the above development, the median survival of patients with mRCC is now approaching 30 months (up from less than one year in 2000) and is poised to increase even further with the preliminary, but very promising results of novel immunotherapy approaches.^{7,8} Many patients are now living with metastatic disease for years as they undergo sequential drug treatments, sometimes surgeries (metastasectomies and/or cytoreductive or palliative nephrectomies) and targeted radiation treatments.^{9,10} Unfortunately, although most patients with mRCC will have some benefit from the above mentioned therapy, virtually all will progress and will thus be in need of new interventions.

[figure not shown]
Scientific Rationale for Combination Ixazomib and IFN in RCC

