4.3 Number of Patients

For the phase I portion of the study we will enroll at a minimum 12 and at a maximum 18 (please see Section 4.1 and 7 for more on the statistical design). For the phase II portion of the study we will enroll up to 31 patients. For phase II portion, a patient is considered enrolled at cycle 1 day 1 when at least one of the drugs has been administered. All patients will be included in the toxicity and PFS and RR analysis.

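### Exclusion 4 prints a three-week washout as a maximum instead of a minimum, and its radiotherapy interval differs from exclusion 6 whichever sign is meant

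*Combined protocol and SAP*

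**What the plan says.** Section 5.2 opens with "Patients meeting any of the following exclusion criteria are not to be enrolled in the study", so the exclusions are cumulative. Exclusion 4 lists washout intervals in three bullets:

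- The first concerns bevacizumab and sets a minimum: "last dose must be \geq 6 weeks prior to day 1 of study treatment".
- The second concerns targeted agents and also sets a minimum, expressed through the drug's elimination: "last dose must be \geq 5 half-lives prior to initiation of day 1 of study treatment".
- The third covers radiotherapy, immunotherapy and any remaining chemotherapy, and here the sign turns round: "Last dose must be \leq 3 weeks prior to day 1 of study treatment".

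Exclusion 6 deals with radiotherapy again: "Radiotherapy within 14 days before enrollment. If the involved field is small, 7 days will be considered a sufficient interval", with the small-field interval counted to ixazomib. Exclusion 19 uses 21 days as a minimum for investigational agents. Exclusion 2 requires recovery from the "reversible effects of prior chemotherapy, radiation therapy or targeted therapy".

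Three other places matter for the clock:

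- Section 4.3 says that in phase II "a patient is considered enrolled at cycle 1 day 1 when at least one of the drugs has been administered".
- Section 5.3.1 has eligible patients entered at registration, with treatment to start within 7 days, and requires a signed eligibility checklist.
- Schedule of Events footnote 2 starts ixazomib in week 2, while pIFN starts in week 1.

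**The concern.** All three bullets of exclusion 4 have the same form, but the third carries the opposite sign. Under the printed rule, chemotherapy, immunotherapy or radiotherapy given the day before day 1 satisfies bullet 3, and the same therapy given four weeks before fails it. A washout rule cannot be meant to work that way.

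The rule is operative. The checklist is signed at registration, and section 10.2 requires the study to be run as described, with deviations needing prior IRB approval except for an immediate hazard. A site that follows the text turns away patients with older therapy. A site that silently reads it as a minimum departs from the written protocol. For immunotherapy that is not investigational, bullet 3 is the only time-based washout, and exclusion 2 does not name immunotherapy.

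Radiotherapy is plausible in this population. Section 1 mentions "and targeted radiation treatments" among the treatments that patients with metastatic disease receive, and inclusion 10 admits brain metastases treated with radiation. Correcting the sign alone would still leave two different radiotherapy intervals in one list.

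**Working it through.** The plan gives no figure to reproduce. The check compares the printed rules in days.

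**Definitions.** D = whole days from last radiotherapy to day 1. g = days from enrollment to day 1: 0 if enrollment is cycle 1 day 1 (section 4.3), and 0 to 7 if it is registration (section 5.3.1). Section 4.3 defines enrollment for phase II only.

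**Rules.**
- Bullet 3 as printed: D ≤ 21. With the sign corrected: D ≥ 21.
- Exclusion 6, standard field: D − g ≥ 15 if day 14 counts as within 14 days, or D − g ≥ 14 if it does not.
- Exclusion 6, small field: at least 7 days to first ixazomib, which falls at about day 8, that is D + 7. Visits from week 2 have a 2-day window (Schedule of Events footnote 1), so the earliest is D + 5.

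**Step 1, as printed, standard field.** Both rules are met for D from 15 + g to 21, which is 7 − g values. If day 14 is outside, the range is 14 + g to 21, which is 8 − g values.
- g = 0: D = 15 to 21, 7 values (or 14 to 21, 8 values).
- g = 7: none, since 15 + 7 = 22 > 21 (or D = 21 only).

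**Step 2, as printed, small field.** D + 7 ≥ 7 gives D ≥ 0; with the early visit, D + 5 ≥ 7 gives D ≥ 2. The upper limit is 21. Radiotherapy almost up to the first pIFN dose would pass both rules.

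**Step 3, sign corrected, standard field.** Bullet 3 first allows D = 21.

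| g | Exclusion 6 first allows D (day 14 within / outside) | Bullet 3 later by |
|---|---|---|
| 0 | 15 / 14 | 6 / 7 days |
| 6 | 21 / 20 | 0 / 1 day |
| 7 | 22 / 21 | −1 / 0 days |

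So bullet 3 supersedes the 14-day rule when g = 0. At g = 7 the two rules coincide, or exclusion 6 is stricter by one day.

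**Step 4, sign corrected, small field.** The minimum is 21 days to day 1, against 7 if the allowance is counted to day 1: 21 − 7 = 14 days longer. On exclusion 6's own clock it is 21 + 7 = 28 days to ixazomib (21 + 5 = 26 with the early visit), against 7. The 7-day figure is therefore never the binding limit. The only case where the exception matters at all is a one-day edge: g = 7, D = 21 and day 14 counted as within, where a small field is excused from the 14-day rule.

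**Step 5, is the sign real?** Sections 5.1 and 5.2 contain 12 ≤ or ≥ signs: 7 in 5.1 and 5 in 5.2. The other 11 read sensibly, including the two just above bullet 3. But section 4.2 prints two signs opposite to their evident intent, in its 8-week and 16-week PFS thresholds. An extraction fault is unlikely but not excluded. Steps 3 and 4 do not depend on it.

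**The case against.** The strongest reply is that everyone knows what is meant. The list is about washout, the neighboring bullets and exclusion 19 are minimums, and in a list of exclusions ≤ 3 weeks is the natural way to describe who is kept out; the slip is joining it to a must-be clause. Harm requires that the sign is truly printed, that the checklist (not provided) copies it, and that staff at the one center apply it against its evident purpose. None of these is shown. This reply stands as to intent and size. It does not make the text correct, and section 10.2 does not allow the presumed meaning to be substituted informally.

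Three stronger readings are tempting, and the documents do not support them.

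- A reader might infer that patients without adequate washout will distort DLT, UT or PFS. But inclusions 6 and 7 (performance status, laboratory limits) and exclusions 2, 6, 14 and 19 partly screen recent therapy, no share of affected patients is given, and the TKIs, mTOR inhibitors and bevacizumab described in section 1 fall under the correctly signed bullets.
- A reader might infer that exclusions 4 and 6 contradict each other. With the sign corrected they are cumulative, and the stricter one applies.
- A reader might infer that the 14-day rule never decides. That needs enrollment to be cycle 1 day 1. Elsewhere the protocol treats enrollment or study entry as coming before dosing: section 5.3.1, and Schedule of Events footnote 13, which requires enrollment before correlative blood that the sample sheet lists as pre-dose on day 1. With a 7-day gap, exclusion 6 can equal or exceed 21 days.

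**Conclusion.** The point holds as a modest eligibility-wording error. Bullet 3 says the reverse of what a washout rule should say, and nothing else in the documents corrects it. Independently of the sign, bullet 3 and exclusion 6 give different radiotherapy intervals. Once the sign is corrected, the small-field 7-day interval never sets the limit.

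The day counts rest on three assumptions: whole-day counting, ixazomib at about day 8, and a stated choice of enrollment anchor. The 6- or 7-day gap for a standard field applies only when enrollment is cycle 1 day 1. No claim is made about DLT, UT, PFS, type I error or power, so the correction is worth making but does not bear on the validity of the design.

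**What to change.** Change ≤ 3 weeks to ≥ 3 weeks in exclusion 4, bullet 3, and make the eligibility checklist match.

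In the same amendment, have the sponsor's clinicians state which radiotherapy interval governs. Either:

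- keep 21 days for all radiotherapy and delete exclusion 6; or
- take radiotherapy out of bullet 3 and let exclusion 6 govern, counted to day 1 of study treatment. The re-anchoring matters: counted to ixazomib, the small-field allowance could permit radiotherapy immediately before the first pIFN dose (step 2).

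The second option shortens the probable 21-day minimum, so it is a clinical choice and not a mere tidying of text.

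Inclusion 10 should be reworded to require definitive brain therapy at least 14 days before registration, if a minimum is meant; its present phrasing can also be read as a maximum.

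The cost is one wording amendment and a revised checklist, with no change to sample size or analysis.
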